3. INCLUSION / EXCLUSION CRITERIA

Screening: We will recruit adult male or female patients with PBH from the hypoglycemia clinic at Joslin (directed [name]). Patients will undergo a history and physical examination, with particular emphasis on inclusion and exclusion criteria. Blood and urine samples will be obtained for screening laboratory testing including hemoglobin A1c, CBC, comprehensive chemistry, and urinalysis. Consent forms will be reviewed in detail with potential participants.

Inclusion criteria:

1. Males or females diagnosed with ongoing post-bariatric hypoglycemia with prior episodes of neuroglycopenia, unresponsive to dietary intervention (low glycemic index, controlled carbohydrate portions) and trial of acarbose therapy at the maximally tolerated dose.
2. Age 18-65 years of age, inclusive, at screening.
3. Willingness to provide informed consent and follow all study procedures, including attending all scheduled visits.

Exclusion criteria:

1. Documented hypoglycemia occurring in the fasting state (> 12 hours fast);
2. Chronic kidney disease stage 4 or 5 (including end-stage renal disease);
3. Hepatic disease, including serum ALT or AST greater than or equal to 3 times the upper limit of normal; hepatic synthetic insufficiency as defined as serum albumin < 3.0 g/dL; or serum bilirubin > 2.0;
4. Congestive heart failure, NYHA class II, III or IV;
5. History of myocardial infarction, unstable angina or revascularization within the past 6 months or 2 or more risk factors for coronary artery disease including diabetes, uncontrolled hypertension, uncontrolled hyperlipidemia, and active tobacco use;
6. History of cardiac arrhythmia or arrhythmia detected by EKG during the screening visit;
7. History of syncope (unrelated to hypoglycemia) or diagnosed cardiac arrhythmia
8. Concurrent administration of β -blocker therapy;
9. History of a cerebrovascular accident;
10. Seizure disorder (other than with suspect or documented hypoglycemia);
11. Active treatment with any diabetes medications except for acarbose;
12. Active malignancy, except basal cell or squamous cell skin cancers;
13. Personal or family history of pheochromocytoma or disorder with increased risk of pheochromocytoma (MEN 2, neurofibromatosis, or Von Hippel-Lindau disease);
14. Known insulinoma or glucagonoma;
15. Major surgical operation within 30 days prior to screening;
16. Hematocrit \leq 33%;
17. Bleeding disorder, treatment with warfarin, or platelet count <50,000;
18. Blood donation (1 pint of whole blood) within the past 2 months;
19. Active alcohol abuse or substance abuse;
20. Current administration of oral or parenteral corticosteroids;
21. Pregnancy and/ or Lactation: For women of childbearing potential: there is a requirement for a negative urine pregnancy test and for agreement to use contraception during the study and for at least 1 month after participating in the study. Acceptable contraception includes birth control pill / patch / vaginal ring, Depo-Provera, Norplant, an IUD, the double barrier method (the woman uses a diaphragm and spermicide and the man uses a condom), or abstinence;
22. Use of an investigational drug within 30 days prior to screening;

23. Current use of anticholinergic medications;

24. Allergy to a component of the study drug.

There will be no involvement of special vulnerable populations such as fetuses, neonates, pregnant women, children, prisoners, institutionalized or incarcerated individuals, or others who may be considered vulnerable populations.

4. DATA ANALYSIS / SUBJECT SELECTION

Subject Selection:

Approximately 40 subjects may be screened for this study, assuming approximately 30% will not meet inclusion criteria, and assuming 20% dropout rate. The goal is for 20 subjects to complete Part 1 and Part 2 studies. To allow for potential drop-outs, 28 subjects will be randomized.

Data Analysis:

All subjects who have received at least one dose of glucagon will be included in the data analysis set. Adverse events, vital signs, physical examination, laboratory safety variables (Screening to Final Visit), EKG (Screening to Final Visit), and local tolerability data will be reviewed and summarized on an ongoing basis during the study to evaluate the safety of subjects. Safety data will be presented in tabular and/or graphical format and summarized descriptively, where appropriate.

Sensor and glucagon or vehicle delivery information will be collected and evaluated for specificity and response time.

Plasma glucagon concentrations will be analyzed by a validated LCMS method in a GLP compliant lab (Celerion, Inc. Lincoln, NE). Insulin and incretin plasma concentration profiles will be analyzed with a commercially available radioimmunoassay method (RIA, Millipore) and analyzed using repeated-measures ANOVA.

The primary endpoint for this study is prevention of meal or exercise-provoked hypoglycemia, defined as glucose levels below <65 mg/dl, compared to vehicle control. Secondary outcome measures will compare outcomes for glucagon versus vehicle infusions for the following metrics including: (1) prevention of severe hypoglycemia (defined as glucose levels below 60 mg/dl); (2) prevention of rebound hyperglycemia (defined as glucose levels above 180 mg/dl); (3) time in goal range (65-180 mg/dl), reported in minutes.

Success will be defined as meeting the primary endpoint in 12 of 20 participants. If this is not achieved, the algorithm will be revised, and an additional 5 participants may be recruited for additional study.

Data will be analyzed after 10 individuals have completed the paired analysis of response to glucagon vs. vehicle. At that time, power will be determined, and sample size will be adjusted if needed.

Local Interim Data Analysis/Data Monitoring Plan

Data will be stored using a secure, web-based application designed to support data capture for research studies (such as RedCap), providing: 1) an intuitive interface for validated data entry; 2) audit trails for tracking data manipulation and export procedures; 3) automated export procedures for seamless data downloads to common statistical packages; and 4) procedures for importing data from external sources. Data are stored and are backed up on a scheduled basis with data encryption for any regulated data types (private health data (PHI) which require backup media in an encrypted format.

Data will be maintained in protected files at Joslin Diabetes Center. Only deidentified data will be transferred (via secure electronic file transfer) between collaborators.

Data Safety Monitoring Plan: This plan will be implemented and strictly followed, and a Safety Officer will be appointed to provide oversight and review. The PI will be responsible for ensuring that recruitment and phenotypic analyses are conducted in accordance with the IRB-approved protocol and

will review all adverse events and serious adverse events. The Joslin study nurse coordinator will also perform a periodic review of all data from phenotypic analyses. The members of the study team will conduct regularly scheduled meeting approximately weekly as well as on an as-needed basis to review status of the trial inclusive of enrollment, oversight of informed consent, general conduct of the trial as well as reporting of any complications as needed to the NIH and IRB. If permission is provided by the patient, the study team will provide a follow up letter to his or her primary care provider or endocrinologist, as needed, to alert them of their patients' participation in the trial and of any clinically significant findings regarding their respective patients. Patients will not be required to provide permission for the study team to contact their primary care provider, or endocrinologist as needed, in order to participate in the study. Patients will also have the option to elect to receive a letter containing clinically significant results from the study team after conclusion of the study.

5. **POSSIBLE BENEFITS:**

The purpose of this study is to evaluate a new approach for the treatment of post-bariatric hypoglycemia. This project is not designed to be of direct benefit to any individual subject, although it is hoped that through the knowledge gained from these studies there will be general benefit to persons with or at risk of development of PBH. Subjects enrolled in this study receive comprehensive medical evaluation. As such, risks are appropriate in relation to the potential significant benefits for the significant number of persons with or at risk for hypoglycemia after bariatric surgery. Thus, the potential benefits to society are likely to outweigh the risks to the individual subject.

6. **POSSIBLE RISKS:**

Risks regarding participation include risks associated with:

Glucagon: Administered in usual rescue dose of 1 mg intramuscularly, glucagon can cause nausea, vomiting, dizziness, and headache, as well as other less common complaints (listed in table below). The doses to be administered in the present study (300 µg) will be less than ½ the usual rescue dose (1 mg).

Likely (≥10 subjects out of 100)	Less Likely (3-9 subjects of	Rare (2 or fewer subjects out of 100)	
Dizziness	Asthenia	Abdominal pain	Pain
Headache	Palpitation	Back pain	Pharyngitis
Nausea	Sweating	Confusion	Pruritis/Rash
Vomiting	Thirst	Diarrhea	Syncope
	Vasodilation	Dyspepsia	Taste perversion

Nonaqueous glucagon is a formulation of glucagon which is stable at room temperature. Previous studies have demonstrated that adverse events were generally mild to moderate in nature and similar to known effects of glucagon. A prior study of mini-dose glucagon (Xeris protocol XSMP-201) used doses similar to those in the current study (0.075 mg, 0.15 mg, and 0.3 mg); the most frequent adverse event was burning sensation at the injection site (58-75% of patients). Mild-to-moderate nausea was observed at the highest dose only (33%), while numbness was observed at injection site in up to 17% of patients. In 2015-28, glucagon administration resulted in local stinging at the site, with no nausea or other side effects reported by patients.

Glucagon Infusion System: This system being tested with this protocol will consist of an Omnipod pump filled with nonaqueous glucagon. The pump will be programmed to receive sensor glucose values transmitted from the Dexcom continuous glucose monitor, and to trigger glucagon or vehicle delivery when prespecified thresholds are reached based on the algorithm. Risks associated with this

system include:

- (1) sensor failure, leading to lack of detection of rapid drops in glucose or hypoglycemia;
- (2) failure of communication between sensor and pump,
- (3) failure of pump to deliver correct dose of glucagon,
- (4) inadequate response to nonaqueous glucagon, resulting in lack of correction of hypoglycemia,
- (5) delivery of excessive glucagon by pump, or excessive response to nonaqueous glucagon, could result in nausea or other side effects of glucagon, including hyperglycemia, potentially triggering subsequent hypoglycemia.

Risks of these complications will be mitigated by the presence of the study physician and nurse in the room, who will monitor patient for signs and symptoms of hypoglycemia, changes in vital signs, and real-time glucose levels, as determined by the in-room YSI glucometer. As noted above, if hypoglycemia develops despite pump delivery of glucagon or vehicle, standard approaches for treatment will be used, including glucose tablets and standard glucagon. In addition, participants will be monitored for 2 hours after glucagon delivery and lunch to ensure stability of glucose before discharge.

Risk of Device Reuse: The Dexcom G4 Platinum Professional continuous glucose monitor is approved for multiple patient use. The sensor (the component of the system that enters the skin) will be single use only. Additional components of the system include the transmitter, which is attached to the sensor but does not enter the skin, and the receiver, a hand-held device. Both the transmitter and receiver will be reused after cleaning using manufacturer-specified disinfection protocols using hospital disinfectant, as described above.

The Omnipod System is labeled for single-patient use. The system is comprised of the Omnipod disposable pump and a handheld Personal Diabetes Manager (not attached to the skin). The participant will not touch or interact with the PDM device. The PDM handheld device will be reused for multiple studies, after adhering to cleaning protocol as described above. All infusion set equipment will be single patient use only.

Glucometers will not be cleaned or reused by subjects. A new meter will be given to each new participant.

IV catheter, sensor, and pump placement may cause bleeding, infection, clot formation (all minimal risk), bruising, or discomfort.

Phlebotomy may cause blood loss and discomfort. For Part 1, the total volume of blood sampling is up to a maximum of 450 ml. (These calculations are based on the maximum possible. The volume will be lower if the patient has hypoglycemia prior to 180 minutes after mixed meal, which typically occurs at 90 minutes; the estimated volume in this more typical scenario would be 269 ml.) This should not pose significant stress to any individual. Screening prior to Part 1 will verify that Hct is over 33 at study entry.

Part 1 and 2 will be separated in time by at least 2 months. Volunteers will be urged to be very consistent with multivitamin supplementation between Parts 1 and 2, which is a typical part of the post-bariatric medication needs long-term. Hemoglobin/hematocrit will be assessed during the screening visit for Part 2; as for Part 1, patients will not be eligible if they are anemic ($Hct \leq 33$). For Part 2, the estimated maximum blood sample volume is 338 ml.

Volunteers will be requested not to donate blood within 2 months of the study. Any subject who has just donated blood will be asked to postpone entry into the study until 2 months have elapsed. Patients previously studied under CHS 2015-28 will not be studied again until at least 3 months have elapsed.

Meal tolerance testing may cause transient nausea or dumping syndrome in post-bariatric hypoglycemia patients. We have performed over 50 meal tolerance tests in this population without complication. Oral intake may also cause hypoglycemia in these patients. However, patients are

unlikely to experience severe low blood sugar because of frequent measurements and protocols in place to treat accordingly. The study physician will be physically present on site in the clinical research unit during testing in order to closely monitor participants and ensure safety.

Exercise Intervention: There is a remote possibility of adverse events including hypoglycemia, abnormal blood pressure, fainting, dizziness, arrhythmia, and in very rare instances, heart attack or stroke. There also exists the risk of bodily injury including injuries to muscles, ligaments, tendons, and joints. To minimize the risk of an adverse event, all participants will be pre-screened by the study physician prior to participation. Specific attention will be focused on history of known cardiac arrhythmias, cardiovascular, cerebrovascular disease or concurrent β -blocker therapy. Participants will be excluded if these conditions are present.

At least one study physician and one study nurse will be present during the exercise portion with careful monitoring of glucose, vital signs and symptoms. The minimum plasma glucose level prior to initiating the exercise should be greater than 75 mg/dl. Exercise will take place on a stationary bicycle which has a low impact on joints and low risk for falls or trauma. Patients will exercise until a threshold of the sensation of exhaustion, max heart rate of $(=208 - (0.7 \times \text{age}) \text{ bpm})$ or 15 minute duration is achieved. Exercise will be halted immediately if the participant develops chest pain or chest pressure, undue shortness of breath, hypotension, feelings of being unwell, signs of poor perfusion (e.g., lightheadedness, confusion, ataxia, pallor, cyanosis, nausea, cold and clammy skin, etc.), Heart rate above the prespecified maximum heart rate of the subject (MHR), drop in systolic or diastolic blood pressure by more than 20 mm Hg as compared with baseline, or if the participant chooses to stop. The study visit will also be halted if the participant develops unremitting nausea, abdominal pain, or wishes to discontinue the study for any reason. In case of an emergency, an emergency medical team will be available on-site at the Joslin Diabetes Center to stabilize the patient prior to transport to Beth Israel Deaconess Medical Center if needed.

Screening Tests and Procedures: It is possible that as a result of the screening process a subject may learn that they have a health disorder that they were unaware they had. Every effort will be made to help the participant obtain the care that they need.

Breach of Confidentiality: While every effort will be made to protect the confidentiality of participant identifiable information, there is the potential loss of confidentiality by participating in this study.

Inconvenience and Unknown Risks: Participants may be inconvenienced by the time commitment involved in participation in the study. There may be other risks from this study not yet identified.

Participants can choose not to participate in the clinical research project and can withdraw consent at any time.

Adequacy of Protection Against Risks

Recruitment and Informed Consent: Subjects will be recruited from the Joslin Hypoglycemia Clinic. The study will be explained to the potential subject initially in the clinical setting or during a subsequent telephone screening session. The informed consent process will be inclusive of various types of education and counseling opportunities including an in-person or telephone screening, allowing for general overview of the procedures as well as options available for all subjects expressing interest in participation.

Those still interested after in person or telephone screening will be scheduled for screening visit(s) at the clinical research center. The consent process will involve initial discussion of the purpose and scope of the research as well as risks and benefits. Ample opportunity will be provided for participants to read consent, share with family or other health care providers as well as have all questions answered by the Principal Investigator or their designated study staff prior to obtaining written informed consent using IRB approved documents. The consent form will include a description of risks and benefits, alternative possible procedures, the availability of the investigating physicians throughout any study to discuss any concerns, the availability of the IRB to the patient throughout any study to discuss any

Approved by

JDC CHS

concerns, and the fact that the patient can withdraw from the study at any time with no change in his/her standard treatment. There can be no changes in the protocol without the prior agreement of the Committee on Human Subjects.

If the patient consents to enroll in the study, and the consent form is signed, further evaluation in the form of the medical and screening visit will take place to determine eligibility. One copy of the consent form will be retained by the principal investigator and one copy will be provided to the subject.

Protections Against Risk: The procedures for minimizing risks are discussed above. Participants will be queried at each visit for potential side effects of testing. Appropriate intervention following standard medical practices will be used in the event of medical complications. The investigators are accountable to the institution's Committee on Human Subjects and must report annually the total experience as well as report immediately any complications.

Safety monitoring will include frequent blood glucose monitoring during study visits by study staff. A study physician will be physically present in the study room at all times to evaluate clinical status and glycemia. All labs will be reviewed by a designated member of the study team within 24 hours. Abnormal labs are communicated by alerts to the principal investigator directly from the laboratory and will be communicated to the participant and treating physician if clinically actionable. Adverse events will be reported to the IRB, FDA, and NIH, as appropriate, to ensure the safety of subjects.

Storage of private health information is solely in locked offices or on secure access protected computer sites and portable devices that may be used for patient data are encrypted to protect privacy. All study staff are trained in privacy protection and the ethical conduct of clinical research.

The study would be halted if the following serious adverse events occur: cardiac arrest, seizure, loss of consciousness, need for emergency transport, severe musculoskeletal injury, stroke, significant hemodynamic crisis including severe hypotension, hypertensive crisis, or any other serious adverse event.

7. CONSENT PROCEDURES:

Subjects will be recruited from the Joslin Hypoglycemia Clinic. The study will be explained to the potential subject initially in the clinical setting or during a subsequent telephone screening session. The informed consent process will be inclusive of various types of education and counseling opportunities including an in-person or telephone screening, allowing for general overview of the procedures as well as options available for all subjects expressing interest in participation.

Those still interested after in person or telephone screening will be scheduled for screening visit(s) at the clinical research center. The consent process will involve initial discussion of the purpose and scope of the research as well as risks and benefits. Ample opportunity will be provided for participants to read consent, share with family or other health care providers as well as have all questions answered by the Principal Investigator or their designated study staff prior to obtaining written informed consent using IRB approved documents. The consent form will include a description of risks and benefits, alternative possible procedures, the availability of the investigating physicians throughout any study to discuss any concerns, the availability of the IRB to the patient throughout any study to discuss any concerns, and the fact that the patient can withdraw from the study at any time with no change in his/her standard treatment. There can be no changes in the protocol without the prior agreement of the IRB.

If the patient consents to enroll in the study, and the consent form is signed, further evaluation in the form of the medical and screening visit will take place to determine eligibility. One copy of the consent form will be retained by the principal investigator and one copy will be provided to the subject.

8. RECRUITMENT / SOURCE OF SUBJECTS:

Patients with post-bypass hypoglycemia will be recruited for this study from the weekly Hypoglycemia

Clinic at Joslin Diabetes Center, directed by [name]. Post-bariatric hypoglycemia syndrome is the most common diagnosis within this clinic. More than 200 patients with this syndrome have been evaluated to date at Joslin, and over 50 patients have participated in research studies to date. Recruitment will be performed in the Hypoglycemia Clinic by the research fellow or nurse.

9. RIGHTS AND PRIVACY:

Storage of private health information is solely in locked offices or on secure access protected computer sites and portable devices that may be used for patient data are encrypted to protect privacy. All study staff are trained in privacy protection and the ethical conduct of clinical research. Records will be made available for inspection by the safety officer upon request.

Please answer the following questions:

- Will medical history/clinical information be obtained from the subjects' medical records for the purpose of this study? If yes, please list what information will be recorded.
 - YES NO
 - Age, gender, race
 - Date of surgery
 - Type of procedure
 - Pre-surgical BMI
 - Concomitant medical problems
 - Active and historical medications
 - History of hypoglycemia: first onset, symptoms, prior treatment approaches

- Will information resulting from this study (i.e. results of clinical/research lab tests, etc...) become part of the subjects' medical record or provided to the subject and/or others for clinical purposes? If, no, please list what information will not be given to the subject or recorded in their medical record and why.
 - YES NO

- Will subjects' identifiable health information* be shared with others outside of Joslin Diabetes Center? If yes, list whom this information will be shared with (please be specific, include names of collaborators, study sponsor contacts)?
 - YES ■ NO

10. OMIT PROCEDURES / LEAVE STUDY:

We will inform patients that they may discontinue the study at any time without consequence. They will be informed that their decision will not affect how they are treated.

11. INCENTIVES / REMUNERATION:

Parking or taxi services will be paid for by voucher on the days of study visits. Other necessary travel expenses will be reimbursed to the participant at the discretion of the principal investigator. In addition

Approved by
JDC CHS 

participants will receive a subject stipend of \$75 for completion of study visit 3 and \$250 for participation and completion of study visit 5.

If this study should result in the development of any marketable product, it is not the policy of the Joslin Diabetes Center to share any profits with participants in the research study.

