research unit. Prior to discharge, the plasma glucose (measured by YSI) must be between 80 and 200 mg/dL on the final two measurements, taken at least 30 minutes apart. If the plasma glucose is between 80 and 90 mg/dL then the CGM trend arrow must be either stable or increasing during the last 30 minutes of observation.

When the standard meal is consumed, the Omnipod® pump will be removed and the site will be assessed visually using the Draize scale. Prior to discharge, the sensors will be removed to permit analysis of timing of alerts and the site of the Omnipod insertion will be reassessed using the Draize scale.

Blood samples collected during this visit will be processed and stored at -80 for subsequent analysis of insulin, glucagon and incretin hormone levels to assess endogenous responses (vehicle delivery days) as well as post-bolus plasma levels (glucagon delivery days). The patient will be called by a study team member within 24 hours of the study visit to collect data for symptoms, glucose values, and any adverse events following study visit.

Between one to two weeks following visit day 3, patient will be scheduled for visit day 5.

Visit Day 4 (Optional): Two to three days prior to visit day 5, patient will have an **optional** visit day 4, during which two Dexcom sensors will be placed on the anterior abdominal wall. If the study team and patient are comfortable with sensor placement, sensor placement can occur at home instead, again 2-3 days before visit day 5. The time of sensor placement will be documented by a phone call by a member of the study team and the study physician will review the medication, food and activity recommendations in preparation for study visit 5.

Study Visit Day 5: Mixed Meal Testing: This visit will be identical to visit 3 with the exception that the patient will receive the other treatment (either vehicle or glucagon) during the mixed meal tolerance test when a hypoglycemic event is predicted by the controller algorithms. As with study visit day 3, the patient will be called by a study team member within 24 hours of the study visit to collect data to survey symptoms, glucose values and for any adverse events following study visit.

Part 2: Testing control system for sensor-guided delivery of glucagon via closed-loop system to prevent post-exercise hypoglycemia in patients with post-bariatric hypoglycemia

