If at any time during the study visit the glucose level falls to or below 55 mg/dl (i.e. as a result of vehicle delivery on vehicle treatment days, inadequate trigger, or inadequate pump-delivered glucagon response), or if the patient develops neuroglycopenia, or if the participant develops severe discomfort with signs and symptoms of hypoglycemia, then the closed-loop pump will be deactivated and treatment for clinically significant hypoglycemia [34] will be initiated. If the participant's previously established IV line is functional, one ampule of D50 (25 grams in 50 mL, 50% glucose solution) will be administered over 2-5 minutes via the intravenous line. Glucose will be re-measured every 5 minutes and intravenous glucose will be given every 15 minutes until blood glucose is > 54 mg/dL and neuroglycopenia is resolved, or more frequently at the discretion of the study physician. If clinically significant hypoglycemia develops and the previously established intravenous lines are non-functional then the study nurse or physician will administer 1.0 mg of commercial glucagon subcutaneously. The study nurse will also attempt to re-establish intravenous access, while glucose will continue to be measured every 5 minutes. Intravenous glucose may be used to resolve persistent neuroglycopenia or for glucose levels ≤ 54 mg/dL. If 2 doses of intravenous glucose are required, an infusion of 10% dextrose will be initiated at a rate of 100 mL/hour, and glucose levels will be monitored every 10 minutes and rate adjustments will be made according to glucose results. Once glucose levels are above 100 mg/dL, intravenous infusion will be tapered with continued monitoring as indicated clinically by the study physician.

If after treatment for clinically significant hypoglycemia the glucose remains < 70 mg/dL but > 54 mg/dL, neuroglycopenia is resolved, and if the patient is able to swallow, then the team will administer oral glucose 15-30 grams (glucose tablets or gel). If the patient is unable to tolerate oral intake (e.g. due to nausea), the team will administer $\frac{1}{2}$ ampule of D50 (12.5 grams in 25 mL) over 2-5 minutes intravenously. Once hypoglycemia has resolved (glucose > 70 mg/dL), neuroglycopenia has resolved, and patient is able to swallow, then the team will provide a standard lunch meal containing complex, low-GI carbohydrates, fat and protein to maintain euglycemia.

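### The only analysis set named requires a dose of glucagon; read plainly, it leaves participants who had only a vehicle visit out of the safety tables

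*Combined protocol and SAP*

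**What the plan says.** Section 4, Data Analysis, opens with the population: "All subjects who have received at least one dose of glucagon will be included in the data analysis set". The next sentence of the same paragraph lists adverse events, vital signs, examination, laboratory and EKG data and local tolerability, which "will be reviewed and summarized on an ongoing basis during the study to evaluate the safety of subjects". The paragraph then states: "Safety data will be presented in tabular and/or graphical format and summarized descriptively, where appropriate". No separate safety population appears in the text available for review.

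In Part 1, each mixed-meal visit carries one treatment. At visit 5, "the patient will receive the other treatment (either vehicle or glucagon) during the mixed meal tolerance test". On timing: "Between one to two weeks following visit day 3, patient will be scheduled for visit day 5".

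The Part 1 paragraph on treating clinically significant hypoglycemia covers glucose at or below 55 mg/dl and names one possible cause: "as a result of vehicle delivery on vehicle treatment days". It also allows commercial glucagon as rescue when the intravenous lines do not work.

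**The concern.** The membership rule depends on one of the two treatments, but safety exposure does not. A participant on a vehicle day has sensors, a pump and intravenous lines placed, goes through a provoked fall in glucose, and may need rescue. The risks listed in section 6 (sensor, communication or pump failure; bleeding, infection or clotting at insertion sites) arise whatever the pump contains.

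Under the stated rule, two participants who leave at the same point are handled differently according to the order they were given. The glucagon-first leaver counts and the vehicle-first leaver does not. If the rule governs the safety tables, the events and local-tolerability scores from the vehicle-first leaver's only treatment visit are missing from them. In a trial of 28, two or three missing participants are a noticeable share, and a poorly tolerated vehicle visit is one plausible reason for leaving.

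**Working it through.** **Inputs (section 4 unless noted).** 40 screened; 30% not eligible; 28 randomized; 20% drop-out; goal of 20 completing Parts 1 and 2; one to two weeks between visits 3 and 5 (Part 1 visit description).

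**Assumptions.** The description of randomization is not in the text available for review, so I take half the participants as vehicle-first. The timing of drop-out is not stated, so I write *s* for the share of leavers who go between visits 3 and 5 and vary it. I also assume that leaving does not depend on order.

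**The plan's own figure.** 40 × (1 − 0.30) = 28, as stated. Expected leavers are 28 × 0.20 = 5.6, and expected completers 28 − 5.6 = 22.4.

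**Who is in the set.**
- Leaves between visits 3 and 5, glucagon first and dosed: in.
- Leaves between visits 3 and 5, vehicle first: out.
- Attends both visits and is dosed with glucagon: in.
- Attends both visits, but the glucagon visit triggers no bolus: out. The plan regards absence of hypoglycemia by 180 minutes as highly unlikely, and the counts below do not include this group.

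**Number left out** = 28 × drop-out × 0.5 × *s*.

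| Leavers | *s* = 1 | *s* = 0.5 | *s* = 0 |
|---|---|---|---|
| 5.6 (20% of 28) | 2.8 | 1.4 | 0 |
| 8 (28 falling to 20) | 4 | 2 | 0 |

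**Exposure at 20% drop-out and *s* = 1.** Participants actually exposed to vehicle: 22.4 + 2.8 = 25.2. Vehicle-exposed within the set: 22.4. Missing: 2.8 / 25.2 = 11% of vehicle visits. Participants exposed to glucagon: 22.4 + 2.8 = 25.2, all within the set.

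**With the set redefined** as everyone who had a device placed or received any study bolus, both treatments keep 25.2 exposed participants and none is lost.

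**The case against.** The strongest reply is that section 4 never says the safety tables use the glucagon-dosed set. The two statements are only adjacent. The ongoing review is for the safety of subjects generally, and the laboratory and EKG data run from screening, which fits poorly with a set that a vehicle-first participant can enter only at visit 5. This stands in part: the link is the plain reading, because no other population is named, but it is an inference. If the sponsor means to tabulate everyone, the plan needs to say so.

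Three stronger readings are tempting, and the documents do not support them.

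- *Harms on vehicle days would go unseen.* They would not. A call within 24 hours of each visit collects adverse events. Under the Data Safety Monitoring Plan the principal investigator reviews all adverse and serious adverse events, with a Safety Officer providing oversight. Under Protections Against Risk, events are reported to the IRB, FDA and NIH as appropriate. None of this depends on a glucagon dose.
- *The adverse-event comparison would be biased against glucagon by a calculable amount.* Section 4 plans descriptive safety summaries. The glucagon-versus-vehicle contrasts it names are glucose measures. The documents give no event rates for completers or leavers. If bad vehicle visits drive leaving, leavers would also not be equally common in the two orders, so no size or direction of bias can be fixed.
- *Losing at least one participant is near certain.* With 14 vehicle-first participants, the chance is 1 − 0.8^14 = 96% only if all drop-out falls between visits 3 and 5. It is 1 − 0.9^14 = 77% if half does, and 0 if none does. The 20% is stated beside a goal of completing both parts, and anyone doing both has at least two months between them and a second screening. Participants lost there have already finished both Part 1 visits.

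One further complication: read literally, a vehicle-only participant rescued with commercial glucagon has received a dose of glucagon and would enter the set. The plan does not settle this.

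**Conclusion.** The point holds as a defect in a population definition. The one set the plan names is unsuitable for safety because membership depends on having reached the glucagon visit. Read plainly, it would leave vehicle-only participants out of the safety tables and keep glucagon-only participants who left at the same point. The consequence is possible under-counting of vehicle-visit, device and procedure events in those tables.

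The size is about 0 to 3 of 28 participants at the plan's 20% drop-out, or up to 4 if eight leave. This rests on an assumed 1:1 order, drop-out unrelated to order, and unknown timing of drop-out. The documents support no estimate of bias between treatments and no suggestion that individual safety oversight is weakened. The change is worth making before the data are analyzed because it is almost free.

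**What to change.** Keep any efficacy population separate, and for safety replace the single-set sentence with wording to this effect:

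- The safety set is every participant who had a study sensor or pump placed or received any study bolus, glucagon or vehicle.
- Adverse events and local-tolerability findings are tabulated by the treatment of the visit at which they occurred, with the number of visits as the denominator.
- Device- and procedure-related events in participants who were never dosed are listed separately.
- Commercial glucagon given as rescue does not count as study glucagon for set membership.

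The cost is a few sentences in the SAP. The plan already collects the events after every visit, so no new data, visits or participants are needed.
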